4.4. Pharmacokinetic Endpoints

Not applicable for this SAP.

4.5. Pharmacodynamic Endpoints

Not applicable for this SAP.

4.6. Additional Safety Endpoints

Additional safety analyses include:

4.6.1. Adverse Events

Other than Grade III or higher adverse events used to define unacceptable toxicity in the primary endpoint, all adverse events will be assessed for their seriousness, relatedness to study treatment, relationship to study discontinuation, and severity according to [CTCAE](#) version 4.03 criteria.

4.6.2. Vital Signs

Length, weight, blood pressure, respiratory rate, pulse, axillary temperature, and pulse oximetry will be collected at every visit. For detailed schedule of events table, see [Table 1](#).

4.6.3. Physical Examination

Physical examination will include review of the following systems: head, eyes, ears, nose, throat (HEENT), lungs/thorax, cardiovascular, abdomen, musculoskeletal, neurologic, dermatologic, lymphatic, and genitourinary.

4.6.4. Laboratory Evaluations

Blood will be collected throughout the study for standard blood chemistry and hematology tests as well as cardiac enzymes. Urine will be collected throughout the study for standard urinalysis exams.

4.6.5. Use of Non-oral Feeding Support

A swallowing test will be performed at baseline and every 6 months to determine if the patient has signs of aspiration. If the test is positive for aspiration, the patient will be recommended to use an alternative method to oral feeding. Once implanted, a non-oral method of feeding support may later be removed. For each placement or removal event, the type of support (type of tube), date of placement, and date of removal will be noted. Actual use of non-oral feeding support will be quantified through the recording of volume, frequency of use, duration, and calories.

4.6.6. Pulse Oximetry

Pulse oximetry will be measured throughout the study through a small infrared light attached to the end of the patient's finger.

4.6.7. Cardiovascular Safety Evaluations

A 12-lead electrocardiograms will be conducted on the schedule of assessment (Table 1). The ECG tracings or ECG machine data will be collected for centralized review and interpretation by a cardiologist.

Additionally, a Holter monitor will be placed 24 hours prior to dose administration through 48 hours after dose administration. On Day -1 to Day 3, serial ECG data will be pulled in triplicate from the Holter monitor at the following time points:

- Pre-dose (within 24 hours prior to gene replacement therapy)
- 2 hours
- 4 hours
- 6 hours
- 8 hours
- 12 hours
- 24 hours
- 36 hours
- 48 hours

Twenty-four hour Holter monitoring will also be performed at the 3, 6, 9, and 12 month visits and every 6 months thereafter.

4.6.8. Immunology

Immunoreactivity to AAV9 and SMN will be measured in antibody titer levels (in 2-fold serial dilutions) as determined by enzyme-linked immunosorbent assays (ELISAs). T-cell response to AAV9 and SMN will be measured in number of spot forming cells per million peripheral blood mononuclear cells (PBMCs) as determined by Enzyme-Linked ImmunoSpot (ELISpot) assays.

4.6.9. Concomitant Medications

Prior and concomitant medications will be captured in the eCRF from two weeks prior to study dosing through the last study visit and coded using the WHO Drug dictionary, version March 2016 C Final 2.

4.6.10. Non-invasive Ventilatory Support

Patients will be assessed by a pulmonologist at the time points specified in the Schedule of Assessments and may be fitted with a non-invasive positive pressure ventilator (e.g., Bilevel Positive Airway Pressure (BiPAP)) at the discretion of the pulmonologist and/or investigator. Non-invasive ventilatory support equipment may be provided by AveXis, Inc. through a third-party vendor (as necessary).

Each patient will be assessed by investigator whether permanent ventilation criteria has been met. If the patient meets the permanent ventilation criteria, the daily hours of ventilation support (including Trilogy) usage will be reported through [REDACTED]. Also, if trilogy BiPap machine is used with SD card, the daily real hours of usage data will be sent to AveXis.

4.7. Health-economics Endpoints

Not applicable for this SAP.

4.8. Other Endpoints

Additional analyses of the two co-primary and other additional endpoints utilizing a natural history cohort as a comparison may be incorporated, as appropriate.

5. ANALYSIS POPULATION

Safety will be assessed based on all patients who underwent gene therapy at day 1. The primary population for the primary and secondary efficacy analyses will be the ITT population. Patients with 1 copy of *SMN2*, pre-symptomatic patients and patients with the *SMN2* gene modifier mutation (c.859G>C) and other permutations outside of those specified in the ITT population will be evaluated separately as part of additional subgroup analyses.

5.1. Safety Population

All patients who underwent gene therapy infusion will be included. All safety analysis will be based on safety population, unless specified otherwise.

5.2. Intent-to-Treat (ITT) Population

The ITT population will consist of symptomatic patients with bi-allelic deletion of *SMN1* (exon 7/8 common homozygous deletions) and 2 copies of *SMN2* without the known gene modifier mutation (c.859G>C) who receive an IV infusion of AVXS-101 at less than 180 days of age. The first three patients enrolled must meet the criteria for the Intent-to-Treat Population.

5.3. Efficacy Completers Population

The efficacy completers analysis population will consist of:

- All treated patients who reach 14 months of age for the survival endpoint or 18 months of age for the endpoint of achievement of functional independent sitting, OR
- All treated patients who meet discontinuation criteria, discontinue the study due to an AE, or experience death

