6.3. Handling Missing Data

All patients in the ITT analysis set will be included in the primary efficacy analysis for a given endpoint provided there are non-missing baseline values. If a patient misses a regularly scheduled visit, every attempt will be made to reschedule a visit within that visit window to obtain evaluations or tests.

[figure not shown]
For co-primary and co-secondary endpoints, missing values will be imputed as non-responsive.

Additional sensitivity analyses will be performed if there is at least 1 missing value. They include:

- An analysis based on completer population, from which the missing value(s) will be excluded.
- An estimate based on missing values imputed as follows:
 - Set the value to nonresponsive, if a patient discontinues the study due to an AE or experiences death for missing data occurring after these events.
 - Set the value based on the last available response, if otherwise.
- An estimate based on multiple imputation may be carried out using last available response, assuming Missing at Random (MAR).

If an endpoint value is a composite “response-type” (such as maintain ability to thrive) at any visit which is missing due to missing values in any of the components, while the patient is still enrolled (this is expected to happen very infrequently), it may still be possible to determine the response status using those component variables that are not missing. In this case, no imputation method is needed. However, if the response status cannot be determined in the presence of missing components, the method of last observation carried forward (LOCF) or non-responsive will be specified explicitly when applied to any of the missing

components. From that mix of actual and carried-forward values, the value of the “response-type” endpoint at 18 months of age will be determined. This type of LOCF method will be known as “LOCF mixed components,” since it is based on calculating the composite value based on a mixture of values at a visit and values carried forward from previous visits.

For the CHOP-INTEND and BAYLEY instruments, rules suggested by the producers of these assessments will be followed in calculating scores when individual question/items may be missing. If these rules are not enough for calculating a score, then the endpoint will be considered as having a missing value, and this missing value may be addressed as specified in the two paragraphs above or left as missing if acceptable.

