13. CHANGE FROM ANALYSIS PLANNED IN PROTOCOL

The co-primary efficacy endpoint defined as the proportion of patients that achieve functional independent sitting for at least 30 seconds at the 18 months of age study visit included the assumption for the true response rate of AVXS-101 being in the range of 30% - 40%, with a sample size of 15 patients (assuming 30% of patients do not qualify for the ITT population or are otherwise excluded from the analysis) which would provide power of > 90% to detect a significant difference with $\alpha = 0.05$ using a 1-sided exact test for a binomial proportion.

However, for this analysis a 1-sided exact test for a binomial proportion will be used with $\alpha = 0.025$. The co-secondary endpoints will also be analyzed in this fashion.

The efficacy completers population definition in the 15 Oct 2017 version of the protocol reflects:

- All treated patients who reach 14 months of age, OR
- All treated patients who meet discontinuation criteria, discontinue the study due to an AE or death

However, for this analysis the efficacy completers analysis population will consist of:

- All treated patients who reach 14 months of age for the survival endpoint **or 18 months of age for the endpoint of achievement of functional independent sitting**, OR
- All treated patients who meet discontinuation criteria, discontinue the study due to an AE, or experience death
 - All treated patients who reach 14 months of age, OR
 - All treated patients who meet discontinuation criteria, discontinue the study due to an AE or death

However, for this analysis the efficacy completers analysis population will consist of:

- All treated patients who reach 14 months of age for the survival endpoint **or 18 months of age for the endpoint of achievement of functional independent sitting**, OR
- All treated patients who meet discontinuation criteria, discontinue the study due to an AE, or experience death

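### The Efficacy Completers set is drawn from all treated patients, so the completer sensitivity analysis in SAP Section 6.3 changes the population along with the missing-data handling and does not isolate the effect of missing data

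*SAP*

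**What the plan says.** Section 5.3 defines the Efficacy Completers set in two bullets. The first admits "All treated patients who reach 14 months of age for the survival endpoint or 18 months of age for the endpoint of achievement" of sitting. The second adds "All treated patients who meet discontinuation criteria, discontinue the study due to an AE, or experience death". Neither refers to ITT. Section 13 repeats both bullets after the words "However, for this analysis the efficacy completers analysis population will consist of". The protocol definition recorded there also starts from all treated patients; the SAP changed only the age condition, which now depends on the endpoint.

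The ITT set is narrower. Section 5.2 begins "The ITT population will consist of symptomatic patients with bi-allelic deletion of" *SMN1*, and goes on to require two *SMN2* copies, no c.859G>C modifier and infusion before 180 days of age. For one-copy patients, pre-symptomatic patients, modifier carriers and others, Section 5 says that "other permutations outside of those specified in the ITT population will be evaluated separately as part of additional subgroup analyses".

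The primary missing-data rule in Section 6.3 is "For co-primary and co-secondary endpoints, missing values will be imputed as non-responsive". The section continues "Additional sensitivity analyses will be performed if there is at least 1 missing value", and the first analysis listed is "An analysis based on completer population, from which the missing value(s) will be excluded". Sections 8.1.1, 8.2.1 and 8.2.2 call on the Section 6.3 analyses in order to check the missing-data assumptions. Section 6.1 names the Efficacy Completers set beside ITT as an efficacy set and makes ITT primary.

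**The concern.** A sensitivity analysis for missing data should keep the patients of interest fixed and change only how their missing values are treated. As Section 5.3 is worded, the completer analysis does two things at once: it leaves out missing values, and it brings in treated patients from outside ITT. If its result differs from the primary result, the reader cannot tell which change caused the difference. If the two agree, one change may have offset the other.

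The set also sits awkwardly beside Section 5.4. As written, completers are all infused patients except those who leave before the landmark age for a reason outside the second bullet. That is close to the All Enrolled population, whose endpoint analyses Section 5.4 calls descriptive. Nearly the same patients would then serve as a check on a confirmatory ITT result.

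**Working it through.** **1. The plan's own figures.** Section 3.7 takes 15 ITT patients with about 30% excluded: 15 × 0.7 = 10.5, so 10 or 11 analysed.
- *Sitting*, null 0.1%, one-sided exact test at 0.025. One sitter is enough to reject: with n = 10, 1 − 0.999^10 = 0.0100 ≤ 0.025. Power is 1 − 0.7^10 = 97.2% at a true rate of 30% and 1 − 0.6^10 = 99.4% at 40%. With n = 11 it is 98.0% and 99.6%. The stated power above 90% reproduces.
- *Survival*, two-sided Fisher test at 0.05, 80% against 25% with the 23 controls of Section 5.5: 82.4% (n = 10) and 84.6% (n = 11) by full enumeration. The stated power above 80% reproduces.

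No stated figure is in dispute. The point concerns set definitions.

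**2. How many patients can be added.** Section 3.7 plans up to 20 treated and projects at least 15 in ITT. At that split 20 − 15 = 5 are non-ITT, or 5/20 = 25% of those treated.

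**3. Direction of each effect.** Let N be the ITT size, R the ITT responders, m the missing ITT values, q the non-ITT patients added and k the responders among them.
- Primary, missing counted as failure: R/N.
- Completers within ITT: R/(N − m). Since m ≥ 0, this is never below R/N.
- Completers as written: (R + k)/(N − m + q), which can lie on either side of R/N.

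**4. Sitting, assumed outcomes.** N = 15, R = 6 (40%, the upper end of the planning range), m = 2, q = 5, no missing values among the five.

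| Analysis | Calculation | Result |
|---|---|---|
| Primary | 6/15 | 40.0% |
| Completers within ITT | 6/13 | 46.2% |
| As written, k = 0 | 6/18 | 33.3% |
| As written, k = 1 | 7/18 | 38.9% |
| As written, k = 2 | 8/18 | 44.4% |
| As written, k = 3 | 9/18 | 50.0% |
| As written, k = 5 | 11/18 | 61.1% |

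The missing-data effect alone is +6.2 percentage points (46.2 − 40.0). As written, the shift runs from −6.7 (33.3 − 40.0) to +21.1 (61.1 − 40.0). With k = 0 or 1 its sign is reversed.

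**5. Survival, only if the completer analysis is also run for it.** Assume 12 of 15 ITT patients event-free with 2 values missing. Primary: 12/15 = 80.0%. Completers within ITT: 12/13 = 92.3%. As written: 12/18 = 66.7% to 17/18 = 94.4%. Against 6 of 23 event-free controls (23 − 17, Section 5.5), the Fisher p-values are 0.0023, 0.0003, and 0.013 to below 0.0001. In this example the estimate moves but significance at 0.05 does not change.

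**6. Reach into the sitting test.** One sitter rejects at n = 15 (1 − 0.999^15 = 0.0149) and still at n = 20 (1 − 0.999^20 = 0.0198). The completer result is therefore about the size and robustness of the estimate and does not decide the test.

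**The case against.** The strongest reply is that an ITT reading is available. Section 6.3 opens with the ITT set and does not use the full defined name of the completer set. Section 8.1.1 calls on the sensitivity analyses just after summarising sitting in ITT, and Section 8.2.2 ends by placing its analyses on ITT. This shows what may have been meant, but it does not settle the text. The closing sentence of Section 8.2.2 covers ventilatory independence only, Section 5.3 holds the only completer definition, and a programmer following it would flag all treated patients. On the ITT reading, Section 5.3 conflicts with Section 8.2.2, and the same correction is needed.

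Other objections stand and limit the point:
- A reader might infer that the analysis no longer tests missing data at all. It still removes the missing values; what is lost is the ability to separate their effect. The carry-forward and multiple-imputation estimates in Section 6.3 and the time-to-event analysis in Section 8.1.2 are not defined on this set.
- A reader might illustrate the problem with no missing data, for example 6/20 = 30% to 11/20 = 55%. That shows the population effect only, in a case where Section 6.3 would not trigger the analysis.
- A reader might assume that the added patients are milder and flatter the result. The SAP gives no outcome figures for them, and the group is mixed, so the direction is open.
- A reader might take it as stated that non-ITT patients will be tested against the PNCR controls. Section 5.5 names that cohort as comparator for ITT, and Section 8.1.2 computes survival in ITT. The mismatch with controls selected on two *SMN2* copies arises only if the survival sensitivity analysis is run on the completer set.
- The five added patients follow from the projected split; the number could be smaller or zero.

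**Conclusion.** The point holds as a defect of definition. The completer sensitivity analysis, read as written, mixes a change of population with a change in missing-data handling and so does not isolate the latter. It also conflicts with the separate evaluation of non-ITT patients in Section 5. In the sitting illustration, a 6.2-point effect of missing data is replaced by anything from −6.7 to +21.1 points. Those figures rest on an assumed 15/5 split, 6 ITT sitters, 2 missing ITT values and complete data in the other five; the extremes are none or all of the five sitting. The defect has an effect only if at least one value is missing and at least one non-ITT patient enters the set. The primary ITT analysis and its hierarchy of tests are untouched. It is worth correcting because the check is otherwise hard to interpret and the correction is small.

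**What to change.** In Section 5.3, and in the operative definition in Section 13, replace all treated patients by ITT patients in both bullets, so that completers form a subset of ITT. Leave the protocol's own bullets in Section 13 as they are, since they record the superseded definition, and list the restriction to ITT there as a further change from the protocol. In Section 6.3, refer to the set by its defined name. If a summary of all treated completers is wanted, keep it under its own label and call it descriptive, in line with Section 5.4.

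The cost is a few words and one population flag. The restricted set is smaller than the pooled one, but the non-ITT patients remain covered by the separate subgroup analyses that Section 5 already plans.

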5.4. All Enrolled Population

The all enrolled population will consist of all patients who receive an IV infusion of AVXS-101. Analyses of endpoints in this population are considered descriptive.

5.5. PNCR Control Population

The PNCR Natural History dataset ([Finkel, 2014](#)) is drawn from a large natural history study performed on a large cohort of 337 patients with any form of spinal muscular atrophy followed at 3 large, internationally recognized tertiary medical centers with significant expertise in the management of SMA (Harvard University/Boston Children's Hospital, Columbia University and the University of Pennsylvania/Children's Hospital of Philadelphia). Previously identified patients followed in PNCR site clinics and newly diagnosed patients were enrolled. All eligible patients were offered participation in the PNCR study. Study visits were scheduled at baseline and at 2, 4, 6, 9, and 12 months and every 6 months thereafter. The SMA standard of care guidelines published in 2007 were used as a basis for providing uniform care among the study sites. For purposes of this study, sitting (for SMA Type 2) was defined as being able to sit independently for >10 seconds;

children who were unable at any point to achieve this milestone were classified as SMA Type 1.

A natural history control population is drawn from the PNCR Natural History Dataset ([Finkel, 2014](#)) consisting of all patients with age of onset \leq 6 months, bi-allelic deletion of *SMN1* (exon 7/8 common homozygous deletion) and 2 copies of *SMN2* for whom enrollment data (retrospective and prospective) is available to determine survival based on the defined criteria. The *SMN2* modifier mutation (c.859G>C) described by Prior and colleagues (Prior, Thomas W., et. al. "A positive modifier of spinal muscular atrophy in the *SMN2* gene." *The American Journal of Human Genetics* 85.3 (2009): 408-413.) was not assessed in the PNCR study cohort. Based on these criteria, 23 patients from the PNCR dataset are included in the control population. Among them, 17 patients reached the combined endpoint of death or the need for a minimum of 16 hours/day of noninvasive ventilation support for a minimum of 14 continuous days by 13.6 month of age. The survival rate at 13.6 months of age is approximately 25% (17/23), of which the control cohort will be used as comparator with ITT population for survival analysis.

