Based upon preliminary results from the ongoing Phase 1 clinical study AVXS-101-CL-101, at least 80% of treated symptomatic patients with bi-allelic *SMN1* deletions and 2 copies of *SMN2* without the *SMN2* gene modifier mutation (c.859G>C) are expected to achieve the co-primary efficacy endpoint of survival through 14 months of age. It is anticipated that 75% of patients in the PNCR [5] population would not survive beyond 13.6 months of age, and that these control patients will represent a 25% survival rate based upon the natural history of the disease. With this efficacy, an enrolled sample size of 15 patients that meet ITT criteria (assuming 30% of patients are excluded from the analysis) would provide power of >80% to detect a significant difference with $\alpha = 0.05$ using a two sample 2-sided Fisher's exact test, comparing to patient-level data drawn from a published natural history observational study dataset with patients who meet the eligibility criteria for this study (bi-allelic *SMN1* deletions, 2 copies of *SMN2*, age of onset ≤ 6 months of age). The natural history observational study dataset was collected by PNCR network from the study performed at three large, tertiary care centers in the United States (Harvard University, Columbia University, Children's Hospital of Philadelphia; PNCR).

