For a participant who develops an acute reversible illness and/or requires perioperative ventilator support, a recovery period not to exceed 21 days following the date of definitive intervention will be instituted. Following this recovery period, the condition will be considered sub-acute and the participant will become evaluable with regards to the surrogate survival endpoint (Requirement of ventilator support of ≥ 16 hours/day for greater than 14 days).

Example: Using this approach it would mean that on day 1, patient A receives definitive intervention for an acute reversible illness resulting in ventilator support for ≥ 16 hours/day. Days 1-21 will be provided to permit recovery from the acute reversible illness. On Day 22, the participant is no longer considered to have an acute illness. Should the participant continue to require ≥ 16 hours/day of ventilator support from day 22 to day 36, he or she shall be considered to meet the surrogate endpoint.

Statistical approach: The proportion surviving event-free to 14 months of age will be computed in the ITT population. Patients who terminate the study prior to reaching 14 months of age for any reason will be considered treatment failures (event).

As a comparator, in a natural history study of SMA Type 1 patients, [Finkel et al \(2014\)](#) estimated that only 25% of SMA Type 1 patients with 2 copies of *SMN2* would survive event-free to 13.6 months of age.

The observed proportion surviving in the current study will be compared to the natural history data [\(5\)](#) of the matching cohort using a two-sample Fisher’s exact test, along with the corresponding 95% confidence intervals.

If status at 14 months of age is coded using variable SURVIVE as 1 if patient survived to 14 months of age without requiring permanent ventilation, and 2 otherwise, then the SAS code to generate the endpoint analysis is:

```
proc format;  
value survive  
1= 'Yes'  
2= 'No'  
;  
Value grp  
1='AVXS'  
2='PNCR'  
;  
run;  
proc freq data=x order=data;  
table grp*survive / measures riskdiff;  
exact fisher / alpha=0.05;  
run;
```

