Time to death or permanent ventilation through 14 months of age is an additional sensitivity analysis. In case if there is at least 1 patient who is event-free, but discontinue study prior to his/her 14 month birthday, a sensitivity analysis, based on the approach for time to event, will be carried out. In this analysis, time to event will be censored at 14 months of age or at the date of discontinuation. The survival rate at 14 months of age will be estimated by Kaplan-Meier method, and survival curves for AVXS treated patients and the PNCR cohort will be compared using log-rank test at significance level of 0.05.

Additionally, the proportion of patients who experience each of the following events by 14 months of age will be summarized:

- Death
- Permanent ventilation

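### PNCR controls enter the survival comparison only if their survival can be determined, a follow-up-dependent condition that may understate control survival by an amount the SAP does not let a reader judge

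*SAP*

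**What the plan says.** Section 5.5 draws the control population from the PNCR natural history dataset. Besides onset by 6 months, bi-allelic SMN1 deletion and two SMN2 copies, a control must be a patient "for whom enrollment data (retrospective and prospective) is available to determine survival based on the defined criteria". The section reports that "23 patients from the PNCR dataset are included in the control population" and that, by 13.6 months of age, "17 patients reached the combined endpoint of death" or the ventilation criterion. It describes enrolment thus: "Previously identified patients followed in PNCR site clinics and newly diagnosed patients were enrolled".

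Section 3.7 plans the comparison on the basis that "these control patients will represent a 25% survival rate", against 80% in treated patients, using a two-sided Fisher's exact test at 0.05.

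For treated patients, Section 8.1.2 says "Patients who terminate the study prior to reaching 14 months of age for any reason will be considered treatment failures (event"), and Section 6.3 adds "For co-primary and co-secondary endpoints, missing values will be imputed as non-responsive". Section 8.1.2 also describes a Kaplan-Meier and log-rank comparison with the PNCR cohort in which "time to event will be censored at 14 months of age or at the date of discontinuation".

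**The concern.** Onset age and genotype are fixed before follow-up begins. Whether survival can be determined is not. A recorded death settles a child's status at once, and so does a fully documented start of permanent ventilation. A child last seen event-free at, say, 9 months remains unsettled. If the condition means known status at the landmark, it keeps the documented early events and removes children who were event-free when last seen. The remaining event-free proportion is then too low. This comparator decides a co-primary hypothesis, and with 23 controls a few children can move the rejection boundary.

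The sensitivity analysis does not repair this. Kaplan-Meier estimation can use censored children, but Section 8.1.2 applies it to the PNCR cohort that Section 5.5 has already filtered. The only trigger it names is an event-free study patient leaving before 14 months. Section 5.5 does not say how many otherwise eligible controls the condition removed, nor whether the six controls without an event were followed to the landmark.

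**Working it through.** **Inputs.** 23 controls and 17 events by 13.6 months (Section 5.5); 80% versus 25% survival, 15 treated patients less 30% excluded, two-sided Fisher test at 0.05, power above 80% (Section 3.7). The number k of otherwise eligible controls left out is not given, so a range is assumed.

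**Step 1: the plan's own figures.** Control survival is (23 − 17)/23 = 6/23 = 26.1%, close to the planned 25%. The fraction 17/23 = 73.9% printed beside the survival rate in Section 5.5 is the event proportion. Exact enumeration of Fisher power at 80% versus 25% with 23 controls gives 82.4% with 10 treated, 84.6% with 11 and 92.9% with 15. The stated power above 80% reproduces.

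**Step 2: upper bound, all k event-free.** Control survival is (6 + k)/(23 + k). Needed is the smallest number of survivors among 15 treated with two-sided p < 0.05. Power is the binomial probability of reaching that number at 80% true survival, with the control counts held fixed.

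| k | Control survival | Needed of 15 | Power | p for 12/15 |
|---|---|---|---|---|
| 0 | 6/23 = 26.1% | 9 | 98% | 0.0023 |
| 1 | 7/24 = 29.2% | 10 | 94% | 0.0031 |
| 2 | 8/25 = 32.0% | 11 | 84% | 0.0079 |
| 4 | 10/27 = 37.0% | 12 | 65% | 0.011 |
| 6 | 12/29 = 41.4% | 12 | 65% | 0.025 |
| 8 | 14/31 = 45.2% | 12 | 65% | 0.031 |
| 9 | 15/32 = 46.9% | 13 | 40% | 0.056 |

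After the 30% exclusion allowance, the number needed of 10 treated moves from 7 to 8 at k = 1 (power 88% to 68%). With 11 treated it moves from 8 to 9 only at k = 3 (84% to 62%). A result of 8/10 loses significance at k = 5 (p = 0.063).

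**Step 3: half of k event-free.** Control survival is (6 + k/2)/(23 + k): 7/25 = 28.0%, 8/27 = 29.6% and 9/29 = 31.0% at k = 2, 4 and 6. The number needed of 15 is 10 in each case (power 94%), and p for 12/15 is 0.003 to 0.004.

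**Step 4: lower bound, all k events.** Control survival is 6/(23 + k): 6/25 = 24.0% at k = 2 and 6/27 = 22.2% at k = 4. At k = 4, p for 12/15 is 0.0008.

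**Step 5: likely size under simple loss.** A simulation assumed exponential survival, 25% true event-free survival, and loss unrelated to prognosis at times uniform over 0 to 13.6 months. Giving 10%, 20% or 30% of children a loss time and excluding the unknowns yields 23.8%, 22.4% and 21.0%, a downward bias of about 1 to 4 percentage points.

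**The case against.** A reader might infer that control survival is understated. The document does not show this, for three reasons.

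- Section 5.5 reports no excluded control and does not say that determining survival means known status at 13.6 months. The wording also fits a narrower aim: having enough records to apply the endpoint definition. On that reading a ventilated child without recorded hours or duration would be left out too. That removes a likely event and pushes control survival up.
- Previously identified patients were enrolled, and survivors are over-represented among such cases. This also raises control survival.
- If some of the six controls without an event were last seen before 13.6 months, 6/23 overstates survival.

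It is also tempting to blame the contrast with the treated arm, where early leavers count as failures. That rule works against the drug and does not cause the problem. Applied to controls, it would lower their survival further (Step 4).

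Nor is the bias zero only when k = 0. With k = 4 and one survivor, control survival would be 7/27 = 25.9%, practically unchanged.

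The larger figures in Step 2 assume that every excluded child stayed event-free, in a population where 17 of 23 did not. Even then, 12/15 remains significant through k = 8. Finally, Section 8.1.2 first introduces the time-to-event analysis without a condition and names the trigger only in the next sentence, so it may be meant to run always.

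All of this stands, and it limits the point to a possible bias. It does not remove the defect: the comparator is selected on a follow-up-dependent condition, and no planned analysis brings excluded controls back.

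**Conclusion.** The concern holds as a design weakness whose effect cannot be sized from the SAP. Control survival may be understated if event-free children were dropped for short follow-up, but k is unknown and the net direction is open.

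The upper bound is control survival of 29.2%, 32.0% and 37.0% at k = 1, 2 and 4, with 10, 11 and 12 treated survivors needed of 15 in place of 9. If half stay event-free, 10 are needed at k = 2, 4 and 6. At the planned 80% survival with 15 treated (12/15), significance is lost only at k = 9, and only in the extreme case. With 10 treated there is less room: one added event-free control moves the boundary. These figures rest on assumed k, fixed control counts and 15, 11 or 10 treated patients.

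The change should be made, because the method is cheap and would settle the question either way.

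**What to change.** In Section 5.5, define the control set by onset age and SMN1/SMN2 genotype only. Report how many patients the availability condition had removed, why, and the age at which each was last known to be event-free. State whether the six event-free controls were followed to the landmark.

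In Section 8.1.2, run the Kaplan-Meier/log-rank comparison on all these controls whether or not a treated patient leaves early, censoring controls last seen event-free before 14 months. Add two Fisher sensitivity analyses, one counting undetermined controls as all event-free and one counting them as all events. Both are needed, because either alone gives only one side of the range.

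The cost is some SAP wording and a little extra analysis of the comparator dataset. The control rate may become slightly less favourable to the drug. If no control was removed and the six were followed to the landmark, a short statement to that effect settles the point.
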